4.1 OVERALL DESIGN

Aim 1: Determine the impact of a biofeedback training program on decreasing asymmetrical vertical ground reaction forces, frontal plane knee range of motion and the peak knee extension moment, known risk factors for secondary ACL injuries.
We will test the hypothesis that our biofeedback program will decrease the risk of secondary ACL injury by improving loading and movement symmetry during the dynamic task of landing from a jump 6 weeks post intervention.

Aim 2: To demonstrate our ability to recruit, retain and determine patient compliance in completing a biofeedback retraining program. We will demonstrate our ability to recruit 40 ACL reconstructed patients and assess study retention and compliance.

Overview: The goal of this single site, pilot randomized clinical trial is to determine the impact of an innovative biofeedback training program on decreasing surrogate measures of secondary ACL injury risk in adolescent athletes. Movement and loading symmetry will be assessed using the limb symmetry index ($LSI = \frac{ABS[Surgical] - ABS[Nonsurgical]}{0.5(ABS[Surgical] + ABS[Nonsurgical])} * 100$)^{2,3,7,34} prior to (baseline) and at two time points following (immediately following training (efficacy), and 6 weeks after (durability)) the biofeedback training program (**Aim 1; Figure 1**).

40 adolescent ACL patients (20 control, 20 intervention) will be recruited. Subjects will be block randomized into either the control arm or the intervention arm at baseline. All intervention subjects will complete an in-person (no home exercises) biofeedback retraining program for 6 weeks (2 times per week) with a focus on improving both load and movement symmetry through the use of tactile and visual feedback (**Figure 1**), which has been reported to be an effective biofeedback intervention²⁶. Finally, this study will demonstrate our ability to recruit subjects, engage them in the novel biofeedback program, and retain them until study completion. The outcomes from **Aim 2** will inform future study designs.

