7.2 PARTICIPANT DISCONTINUATION/WITHDRAWAL FROM THE STUDY

Participants are free to withdraw from participation in the study at any time upon request. An investigator may discontinue or withdraw a participant from the study for the following reasons:

- Pregnancy
- Significant study intervention non-compliance
- If any clinical adverse event (AE), or other medical condition or situation occurs such that continued participation in the study would not be in the best interest of the participant
- If the participant meets an exclusion criterion (either newly developed or not previously recognized) that precludes further study participation
- Study participant sustains an ACL tear of either limb
- Participant unable to attend the ACL Biofeedback intervention session for 2 days/weeks

The reason for participant discontinuation or withdrawal from the study will be recorded on the Case Report Form (CRF) (MOOP Appendix K). Subjects who sign the informed consent form

and are randomized but do not receive the study intervention may be replaced. Subjects who sign the informed consent form, and are randomized and receive the study intervention, and subsequently withdraw, or are withdrawn or discontinued from the study, will be replaced.

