9 STATISTICAL CONSIDERATIONS

9.1 STATISTICAL HYPOTHESES

All statistical analysis will be completed under the direction of [name]. Depending on the outcome, change (completion-baseline), or the value at completion will be assessed, and the statistical significance of the group differences can be assessed by a t-test or the non-parametric equivalent (2-sample Wilcoxon). Standardized differences will be calculated for the purposes of powering the subsequent clinical trial.

- **Primary Efficacy Endpoint(s):**
We will test the hypothesis that our biofeedback program will decrease the risk of secondary ACL injury by improving loading and movement symmetry (knee extension moment asymmetry) during the dynamic task of landing from a jump 6 weeks post intervention.

Movement and loading symmetry will be assessed using the limb symmetry index ($LSI = \frac{ABS[Surgical] - ABS[Nonsurgical]}{0.5(ABS[Surgical] + ABS[Nonsurgical])} * 100$)^{2,3,7,34} prior to (baseline) and at two time points following (immediately following training (efficacy), and 6 weeks after (durability)) the biofeedback training program.

- **Secondary Efficacy Endpoint(s):**
No hypothesis testing will be completed for the secondary endpoint as this is a pilot clinical trial and will be used to determine the best procedures to following when planning a subsequent multi-center clinical trial. Therefore, we will demonstrate our ability to recruit 40 ACL reconstructed patients and assess study retention and compliance.

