9.2 SAMPLE SIZE DETERMINATION

This is a pilot study, with the purpose of discerning parameter estimates for use in powering a subsequent multi-center clinical trial. To estimate statistical power for this pilot design, we consider a comparison of outcomes by group across time. Previous studies have not examined the knee extension moment limb symmetry index, therefore the difference in knee joint position and the knee extension moment will be employed as proxy variables in order to estimate statistical power for this pilot design. We considered a comparison of outcomes between pre- and post-intervention^{17,18} and side-to-side differences in ACL-R patients. (Table 4).¹⁵

Using 2-sided testing between groups based on previous results, we will need 14 patients overall randomized at 1:1 ratio assuming 80% power to detect a significant difference in the knee extension moment between the groups with $\alpha=0.05$.¹³ Therefore, with recruitment of 40 subjects (goal of retaining 30

Table 4: Sample Size Calculations (N=sample size per group)

	Pre-intervention	Post-intervention	Sample Size
Peak Knee Extension Moment ¹⁰	3.7 ± 0.9	2.4 ± 0.5	N=7
Peak Knee Flexion ¹⁸	88.8 ± 8.0	105.0 ± 5.6	N=5
	Control	Intervention	Sample
Knee Flexion Angle ¹⁸	83.5 ± 20.5	103.8 ± 16.3	N=15
Vertical ground reaction force ¹⁸	2.0 ± 0.4	1.6 ± 0.3	N=14

subjects through study completion), we are adequately powered to declare significance. Thus, while not the primary purpose of this experiment, we are adequately powered to declare significance between groups.

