9.3 POPULATIONS FOR ANALYSES

The following populations will be included in the statistical analysis:

- Modified Intention-to-Treat Analysis Dataset (participants who completed at least 50% of the intervention visits in the Biofeedback Arm of the study and who attended at least one of the post-intervention assessment visits)
- Safety Analysis Dataset: defines the subset of participants for whom safety analyses will be conducted (participants who completed at least intervention visit)
- Per-Protocol Analysis Dataset: defines a subset of the participants in the full analysis (ITT) set who complied with the protocol sufficiently to ensure that these data would be likely to represent the effects of study intervention according to the underlying scientific model (participants who completed at least 80% of the study intervention visits)
- Other Datasets that may be used for sensitivity analyses

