9.4.2 ANALYSIS OF THE PRIMARY EFFICACY ENDPOINT(S)

The goal of the proposed study is to determine the impact of an innovative biofeedback training program on decreasing risk factors for secondary ACL injuries in adolescent athletes. Based on

previous work, the primary variable of interest and a surrogate for secondary ACL injury risk will be the knee extension moment limb symmetry index (LSI). The previously established movement asymmetry risk factors³² and therefore the primary measures of interest are the knee extension moment, vertical ground reaction force, and frontal plane knee range of motion. Symmetry between the operative and non-operative limbs in this study will be determined by calculating the limb symmetry index (LSI). Asymmetry in the peak knee extension moment has been identified as significant predictors of secondary ACL injuries (therefore reduction in this asymmetry will decrease the risk for secondary ACL injuries).³²

For **Aim 1** of this pilot study a within subject repeated measures assessment (ANOVA), as implemented under mixed models, will be used to determine if a clinical (LSI>90%) and/or statistical difference exists between the pre- and the two post-intervention time points (efficacy and durability) for the primary outcome of interest (knee extension moment asymmetry). Post-hoc testing will be completed for any variable that is determined to be statistically different.

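### The between-arm test may rest only on participants with a week-12 value, although the plan allows for 10 of 40 not being retained

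*Combined protocol and SAP*

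**What the plan says.** - **Expected loss.** Section 4.1: "40 adolescent ACL patients (20 control, 20 intervention) will be recruited". Section 9.2: "with recruitment of 40 subjects (goal of retaining 30" through study completion).
- **Group comparison.** Section 9.1: "change (completion-baseline), or the value at completion will be assessed", depending on the outcome, by t-test or two-sample Wilcoxon. The hypothesis in the same section is set at 6 weeks post intervention, which is the week-12 visit. Section 4.4 ties study completion to the last scheduled visit.
- **Model.** Section 9.4.2 names a within-subject repeated-measures ANOVA, fitted under mixed models, which "will be used to determine if a clinical (LSI>90%) and/or statistical difference exists between the pre- and the two post-intervention time points". It does not mention an arm term or an arm-by-visit term.
- **Analysis sets.** The modified ITT set in Section 9.3 requires at least 50% of intervention visits, stated for the biofeedback arm, "and who attended at least one of the post-intervention assessment visits". For sensitivity analysis it mentions only unspecified other datasets.
- **Withdrawal and replacement.** Section 7.2 lists grounds on which the investigator may withdraw a participant, among them "Study participant sustains an ACL tear of either limb". Treated participants who withdraw are to be replaced. Whether their data stay in the analysis is not stated.
- **Missing values.** No section gives a missing-data assumption, an imputation method or a rule for an unobserved LSI.

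**The concern.** A two-sample test on the completion value discards a participant who has baseline and week-6 data but no week-12 test. If people who are doing poorly at week 6 are less likely to return, the remaining week-12 values look too favourable. The effect need not cancel between arms. The attendance condition in the modified ITT set and the withdrawal ground for being unable to attend sessions both name the biofeedback arm. Replacement adds to this, because a participant who did badly can leave the analysed group and a new one can enter.

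The trial's stated purpose is to supply parameter estimates for powering a multi-center trial. An arm difference taken from a selected group would carry into that design.

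**Working it through.** **1. The plan's own figures.** Section 9.2: "Using 2-sided testing between groups based on previous results, we will need 14 patients overall randomized at 1:1 ratio assuming 80% power". From Table 4, the peak knee extension moment is 3.7 (SD 0.9) against 2.4 (SD 0.5). Pooled SD = sqrt((0.81 + 0.25)/2) = 0.728, so d = 1.3/0.728 = 1.786. The noncentral-t calculation gives 7 per group, or 14 overall, as stated. With 15 per arm, power for that proxy is 0.997. The issue is therefore who is analysed, not power on the plan's own inputs.

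**2. Planned loss.** (40 - 30)/40 = 25%, or 5 of 20 per arm if losses split evenly. The documents do not give the split.

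**3. Bias in the completion value.** Assumptions, none of them in the documents: LSI as a surgical/non-surgical percentage, SD 12, week-6 to week-12 correlation r of 0.5 to 0.7, normal values. In the biofeedback arm 25% are lost with a logistic dependence on week-6 LSI (slope 1.0 or 1.5 per SD, low values more likely to be lost). Control loss is random.

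Bias of the completer mean at week 12 = r × SD × E[Z | retained], where Z is the standardised week-6 LSI. E[Z | retained] is 0.213 for slope 1.0 and 0.277 for slope 1.5.

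| Slope | r = 0.5 | r = 0.7 |
|---|---|---|
| 1.0 | 0.5 × 12 × 0.213 = 1.3 | 0.7 × 12 × 0.213 = 1.8 |
| 1.5 | 0.5 × 12 × 0.277 = 1.7 | 0.7 × 12 × 0.277 = 2.3 |

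With random control loss, the arm difference shifts by the same 1.3 to 2.3 points.

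**4. The alternatives under the same assumptions.**
- *Change from baseline in completers.* Under compound symmetry, baseline has the same correlation with week 6 as week 12 has. Both means shift by r × SD × E[Z | retained], and the shift cancels.
- *Likelihood mixed model using week 6.* Loss depends on an observed value, so it is missing at random and the bias is about 0.

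**5. Share meeting the LSI criterion, if reported.** With n randomised, m missing and s observed successes in an arm, the all-randomised rate lies between s/n and (s + m)/n, a width of m/n.
- At 5 missing of 20, the width is 5/20 = 25 points. For example, 8/15 = 53% in completers is compatible with 8/20 = 40% up to 13/20 = 65%, about 13 points down or 12 up.
- For the arm difference, the width is (m1 + m2)/20 = 10/20 = 50 points, however the 10 losses split. For example, 9/15 against 5/15 (+26.7 points) is compatible with 9/20 - 10/20 = -5 up to 14/20 - 5/20 = +45 points.
- Under the step 3 assumptions and a true 50%, completers show 54% to 58%. Counting missing as not met gives 41% to 43% in biofeedback and 0.75 × 50% = 37.5% in control, a spurious difference of 3.5 to 5.5 points.

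**6. Scale of the criterion.** Under the LSI formula printed in Sections 4.1 and 9.1, equal limbs score 0. A score of 90 needs a surgical/non-surgical ratio of (1 + 0.45)/(1 - 0.45) = 2.64, and a ratio of 0.9 scores -10.5. The threshold above 90% presupposes a different scale.

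**The case against.** The best defence is that the plan already names mixed models in Section 9.4.2. A likelihood fit would use a participant with only a week-6 visit, and the modified ITT set admits that participant. Section 9.1 says only that a t-test or Wilcoxon can be used, and its first option, change, was unbiased in the check. Data collection is also protected: stopping the intervention does not end follow-up (Section 7.1), those who withdraw are encouraged to complete assessments (Section 5.5), and missed visits are rescheduled (Section 7.3). Thirty is a goal. Section 9.4.3 defines retention as attending every biomechanical session, so a participant who is not retained may still have week-6 data.

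This stands, and it limits the point to the completion-value option, the analysis sets, and the absence of a named between-arm model. It does not close the gap. The described model compares pre with post, the text does not say that it uses all randomised participants, and the completion-value test remains permitted.

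A reader might also infer three stronger claims that the documents do not support:
- *That success rates rest on completers and can move by 25 points per arm.* No success-rate endpoint is defined. The 25 points is the width of a best-to-worst range under an assumed 5/5 split, not the shift from the completer rate.
- *That counting missing as not met would be a conservative main estimate.* Step 5 shows that it is neither accurate for the rate nor conservative for the comparison.
- *That ACL tears between weeks 6 and 12 will drive the loss.* Tear is a withdrawal ground, but the documents give no tear rate for that window.

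**Conclusion.** The concern holds in limited form. The plan foresees up to 25% not retained, yet it permits a between-arm test confined to observed completion values and does not designate a between-arm model on all randomised participants. Under the assumptions in step 3, the cost is a completer mean about 1.3 to 2.3 points too high at week 12 in the arm with selective loss. The direction favours whichever arm loses its poorer performers. The figure applies to the completion-value option only.

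A likelihood model handles loss that depends on observed visits. It does not remove bias from loss driven by unobserved values, such as those of participants with no post-intervention visit, so loss reasons by arm are still needed. This is a change that should be made, not a flaw that invalidates the pilot.

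**What to change.** 1. In Sections 9.1 and 9.4.2, make the between-arm analysis of knee extension moment LSI one likelihood-based mixed model with arm, visit and arm-by-visit. Use every available visit of all randomised participants, including those later replaced. The week-12 arm contrast tests the hypothesis in Section 9.1. State the missing-at-random assumption.
2. Delete the t-test/Wilcoxon on the completion value. Keep the modified ITT and per-protocol sets as sensitivity analyses.
3. Reconcile the printed LSI formula with the 90% threshold before any share meeting the criterion is computed.
4. If that share is reported, present it descriptively with the number observed, best- and worst-case bounds on all randomised participants, and loss reasons by arm. Do not make missing-as-not-met the main estimate.

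The cost is revised SAP wording, a few table rows and slightly more analysis work. No extra visits or participants are needed.

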5.2 EXCLUSION CRITERIA

An individual who meets any of the following criteria will be excluded from participation in this study:

1. For females: currently pregnant or planning to become pregnant
2. History of more than one ACL reconstruction
3. Post-operative complications that required additional surgical intervention
4. Hospitalization for any reason other than the ACL reconstruction in the last 3 months
5. Plans for additional surgical procedures in the next 12 months
6. Live greater than 60 miles from the research lab
7. Have limitations that would prevent them from attending the biofeedback training sessions
8. Motor neuron diseases, Parkinson's disease, multiple sclerosis
9. Severely impaired hearing or speech (patients must be able to respond to phone calls)
10. No access to a telephone
11. Participating in another ACL intervention outside of standard post-operative physical therapy
12. Attending post-operative physical therapy more than 2 times per week at the time of study enrollment.
13. Inability to understand or speak English (since this will be required for the patient-based intervention)
14. Other self-reported medical problem that would prohibit participation in the study
15. Other health condition or personal issue judged by a study team member or primary care physician to make the patient inappropriate for study participation
16. Knee extension moment limb symmetry index (LSI) greater than or equal to 90% at the time of the initial study assessment

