Landing trial: Subjects will be asked to complete 10 trials of a vertical stop-jump task. During the vertical stop-jump task, subjects will run straight forward for up to 5 steps taking off on 1 foot, landing on 2 feet (one foot on each force plate), and taking off again on 2 feet.^{16,18,20,21} Prior to testing maximum jump height will be determine using a vertec. During testing, a ball will be hung above the force plates at 75% of the subject's maxmum jump height to provide a target during jumping. Subjects will be instructed to jump up and grab the ball and then come down bilaterally on the two force plates. No instructions will be provided on how to land or what to do with their arms to initiate the jump. The stop-jump task will be used to determine if the biofeedback intervention is effective at decreasing secondary ACL risk factors as these risk factors were determined during landing. Subjects will be allowed to practice the task between 3 and 5 times until they are comfortable with the movement. A minimum of 5 minutes' rest will be given between conditions to minimize the effects of fatigue. If the results of the baseline jumping assessment indicates that the subject has a limb symmetry index (LSI) of greater than or equal to 90%, which is indicative of limb symmetry during hopping in healthy subjects, he/she will be excluded from the intervention.

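### Section 9.4.2 accepts passing 90% symmetry, or a pre-post change with no arm term, as a difference, although entry required a baseline below 90% on the same test

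*Combined protocol and SAP*

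**What the plan says.** - **Entry.** Section 5.2, criterion 16, excludes a patient with "Knee extension moment limb symmetry index (LSI) greater than or equal to 90% at the time of the initial study assessment". Section 8.2 (landing trial) applies the rule when "the baseline jumping assessment indicates that the subject has a limb symmetry index (LSI) of greater than or equal to 90" per cent, and justifies the figure as one "which is indicative of limb symmetry during hopping in healthy subjects".
- **Primary analysis.** Section 9.4.2 uses "a within subject repeated measures assessment (ANOVA), as implemented under mixed models" to "determine if a clinical (LSI>90%) and/or statistical difference exists between the pre- and the two post-intervention time points". It names no arm or arm-by-time term. It does not say whether the 90% line applies to a patient or to an arm mean, what proportion would be needed, or how the controls enter.
- **Between-group test.** Section 9.1 says that, on change or completion value, "the statistical significance of the group differences can be assessed by a t-test or the non-parametric equivalent (2-sample Wilcoxon"). It does not mention the 90% line, and Section 9.4.2 does not refer back to it.
- **Caution on claims.** Section 9.4.9 promises a cautionary note for effects declared significant. It is silent on a finding that is clinical only.
- **Scale.** Sections 4.1 and 9.1 print LSI as a difference between limbs divided by their average, which is 0 at symmetry.

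**The concern.** The variable, test and visit that decide eligibility also supply the pre value of the primary outcome. A patient is selected partly because that one reading happened to be low, so the next reading tends to be higher without any training effect. As the rule is evidently meant, the share above 90% starts at 0% and cannot fall.

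Ordinary recovery acts in the same direction. Entrants are about six weeks from release to full sport (Section 5.1) and usual care continues (Section 6.1.1).

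Section 9.4.2 offers two routes to a difference, and both are open to this. Passing 90% is a level reached, not a difference, and the ANOVA does not test it; the and/or wording lets it stand without significance. The statistical route is a pre-post comparison that carries the same selection effect. Either could credit biofeedback with a change that the controls show equally. That would mislead the planning of the multi-center trial that this pilot is meant to inform.

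**Working it through.** The documents give no rate at which patients cross 90% by chance, so there is no figure of the plan's own to reproduce on this point. The Table 4 sample sizes (7, 5, 15 and 14 per group) do reproduce with a two-sample t-test, but they do not bear on it.

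**Inputs from the documents.** Entry below 90; success above 90; 20 patients per arm ("40 adolescent ACL patients (20 control, 20 intervention) will be recruited"); 30 of 40 expected to complete, taken here as 15 per arm.

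**Assumptions.** LSI as a ratio (surgical/non-surgical × 100), bivariate normal across visits, equal mean μ and SD σ, between-visit correlation ρ, no true change. Section 9.2 notes that this index has not been studied before, and Section 9.4.3 plans to estimate its reliability, so a range is shown.

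**1. Patients crossing 90 at one visit.** Let a = (90 − μ)/σ. Then P(post > 90 | pre < 90) = [Φ(a) − Φ₂(a, a; ρ)]/Φ(a). For μ = 80 and σ = 15, a = 0.667 and Φ(a) = 0.7475.
- ρ = 0.5: (0.7475 − 0.6170)/0.7475 = 17.5%.
- ρ = 0.85: (0.7475 − 0.6772)/0.7475 = 9.4%.
- Over μ = 70 to 85 and σ = 12 to 20, same range of ρ: 2% to 27%.
- With 5 points of recovery in both arms (μ = 80, σ = 15): 20% to 28%.

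**2. Mean change.** The entry mean is μ − σφ(a)/Φ(a) = 80 − 15 × 0.3194/0.7475 = 80 − 6.4 = 73.6. The expected rise is (1 − ρ) × 6.4, which is 3.2 points at ρ = 0.5 and 1.0 at ρ = 0.85.

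**3. Pre-post test in one arm.** A simulated paired t-test with 15 patients and no true change rejects in about 7 to 13% of trials at μ = 80, σ = 15, and about 5 to 24% over the grid, against a nominal 5%. A pre-post test pooling both arms would be inflated further, because the same bias is tested with more patients.

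**4. Arm-mean reading.** From step 2, the post mean is about 74.6 to 76.8, well short of 90. Across the grid, the mean of 15 exceeds 90 in under 1% of simulated trials.

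**5. Between-arm comparison.** With 15 per arm and no effect, simulated at means of 75 to 85, SDs of 15 to 20 and reliability of 0.6 to 0.9, a t-test on change rejects in 4.5 to 5.5% of trials. Fisher's test on the proportion above 90 rejects in at most 1.6%.

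**6. Printed formula.** With r the surgical/non-surgical ratio, LSI = 200(r − 1)/(r + 1). Perfect symmetry gives 0. A ratio of 0.90 gives 200 × (−0.10)/1.90 = −10.5. LSI = 90 requires r = 290/110 = 2.64. Read literally, the exclusion would remove almost nobody and the success line would almost never be reached.

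**The case against.** The strongest reply is that the randomised control arm already protects the trial. Both arms share the regression to the mean and the recovery, Section 9.1 offers a between-group test, and Section 9.2 speaks of two-sided testing between groups. Step 5 confirms that such a comparison stays at or below its nominal level. This stands, and it is why the repair is small. But Section 9.1 says only that group differences can be assessed, and Section 9.4.2, which specifies the primary analysis, ties neither its criterion nor its model to that test.

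Second, a repeated-measures model compares means, so the 90% line may refer to an arm mean, which noise does not reach. That is a fair reading, but the text does not state it, and the ambiguity itself needs settling.

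Third, Section 9.2 says that the purpose is parameter estimates and that significance is secondary. That limits the damage. It does not make a pre-post estimate affected by selection a good planning input.

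Two stronger readings should be resisted. A reader might infer that the problem survives whatever LSI scale is used; step 6 shows that it does not arise on the printed formula. A reader might also compute the chance that at least one completer crosses 90% and treat it as a false-success rate; the plan never makes one responder a trial success.

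**Conclusion.** The point holds in a conditional form. What rests on the text alone is this: entry and the clinical criterion share one measure and one cut-off, the entry reading is also the pre value, and Section 9.4.2 accepts either route without requiring a comparison with controls.

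The size rests on assumptions. On a ratio-type scale, read per patient, 9 to 18% cross at one visit with no effect (mean 80, SD 15, correlation 0.85 to 0.5), and 2 to 27% over the wider grid. The one-arm pre-post test is inflated to about 5 to 24%. On the arm-mean reading, the clinical criterion is almost never met by noise. The documents do not support saying that a false claim will be made. They support saying that Section 9.4.2 as written does not prevent one, and that the between-arm comparison would.

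**What to change.** 1. First reconcile the printed LSI formula (Sections 4.1 and 9.1) with the 90% cut-offs in Sections 5.2, 8.2 and 9.4.2, so that all use one stated scale.
2. In Section 9.4.2, remove the clinical (LSI>90%) and/or alternative as a basis for concluding that a difference exists.
3. Rest the Aim 1 conclusion on the between-arm difference in LSI: an arm-by-time contrast from the mixed model, adjusted for baseline LSI.
4. Report the proportion of patients above 90% in each arm at each post-intervention visit, with the between-arm difference and a 95% confidence interval, as supportive only.
5. State that crossing 90% within one arm is not evidence of effect, because entry required less than 90% on the same test.

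The cost is a change of wording, one extra table, and the loss of a claim that is easy to meet. No new data are needed.

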9.4.9 EXPLORATORY ANALYSES

Over the course of the study secondary outcomes will be examined to determine any mediating effects these variables may have, which could explain differences across time (**Table 3**). Secondary outcomes will be evaluated using exploratory analyses in order to generate hypotheses for future studies. These exploratory analyses will be conducted using linear mixed models.^{23,35,36} We will test both primary and secondary outcomes at an alpha level of 0.05 and will not control for potential Type-I errors due to multiple testing, using Bonferroni or Hochberg criteria,^{8,9,19} due to the pilot nature of this study. If an effect is declared 'significant' we will provide a cautionary note in resulting publication, as to the exploratory nature of the findings.

Table 3: Outcome Measurements

Primary Outcomes
Peak Knee Extension Moment Symmetry
Secondary Outcomes
Peak Vertical Ground Reaction Force Symmetry
Vertical Ground Reaction Force Impulse Symmetry
Frontal Plane Knee Range of Motion
Peak Knee Flexion Angle Symmetry
Peak Knee Flexion Angle
Peak Knee Valgus

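### In 9.4.2 the hypothesised week-12 contrast on the primary endpoint sits behind an unneeded overall test across three visits, and the ungated t-test in 9.1 is not named as the primary analysis either

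*Combined protocol and SAP*

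**What the plan says.** Section 9.4.2 assigns the knee extension moment limb symmetry index (LSI) a within-subject repeated-measures ANOVA, fitted as a mixed model, comparing baseline with two post-intervention visits. The next step is conditional: "Post-hoc testing will be completed for any variable that is determined to be statistically different". No arm or arm-by-visit term is named.

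Section 9.1 places the primary hypothesis at one time: "during the dynamic task of landing from a jump 6 weeks post intervention". By the schedule in 1.3 that is the week-12 assessment. The same section says, for outcomes in general and for either change or the completion value, that "the statistical significance of the group differences can be assessed by a t-test or the non-parametric equivalent (2-sample Wilcoxon"). It also promises standardized differences for planning the next trial, with no condition attached.

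Section 9.2 sizes the trial on a group comparison: "Using 2-sided testing between groups based on previous results". Section 9.4.9 sets the level, "We will test both primary and secondary outcomes at an alpha level of 0.05", and declines multiplicity control. No section says whether the 9.1 test or the 9.4.2 model is the primary analysis.

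**The concern.** The hypothesis concerns one contrast at one visit, a 1-df question. Section 9.4.2 puts a 2-df question first, whether anything differs across three visits, and makes specific comparisons only if the answer is significant. The contrast must then clear two tests instead of one, so its power can fall but cannot rise. The gate serves no stated error-control purpose, because 9.4.9 declines adjustment.

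Two things are at stake. One is power for the hypothesised contrast. The other is certainty that this contrast and its interval will be reported, which matters because 9.2 gives the trial's purpose as obtaining parameter estimates for a larger study.

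**Working it through.** **Inputs from the documents.** Two-sided alpha 0.05 (9.2, 9.4.9); 80% power and 14 patients in all at 1:1 (9.2); peak knee extension moment 3.7 ± 0.9 and 2.4 ± 0.5 (Table 4); 40 recruited and 30 to be retained (9.2), so 15 per arm if dropout is equal; three visits (9.4.2).

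**Assumed.** Compound symmetry with between-visit correlation 0.5 or 0.7. The documents give no correlation and no LSI effect or SD; 9.2 says "Previous studies have not examined the knee extension moment limb symmetry index".

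**Step 1: the plan's own figure.** Pooled SD = √((0.9² + 0.5²)/2) = √0.53 = 0.728. d = (3.7 − 2.4)/0.728 = 1.786. A two-sample t-test with noncentrality d√(n/2) needs 7 per group (power 0.865), which is the plan's 14 overall. With 15 per arm the same d gives power 0.997. The effect that gives 80% power with 15 per arm is d = 1.06.

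**Step 2: direct and gated tests.** Section 9.4.2 has no arm term, so the check adds the one that 9.1 and 9.2 imply.
- Overall test: arm-by-visit F on 2 and 2(2n − 2) = 56 df.
- Direct test: t = [(B12 − B0) − (C12 − C0)] / √(4·MSE/n) on 56 df, where B and C are the biofeedback and control means at week 12 and baseline.
- Gated test: the direct test, counted only when the F-test is also significant.

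Simulated power (20,000 runs per case, 15 per arm, correlation 0.5, d in units of the SD of change):

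| d | Week-6 effect ÷ week-12 effect | Overall F | Direct | Gated | Loss (points) |
|---|---|---|---|---|---|
| 1.06 | 0 | 0.841 | 0.812 | 0.770 | 4.2 |
| 1.06 | 0.5 | 0.719 | 0.813 | 0.708 | 10.5 |
| 1.06 | 1.0 | 0.838 | 0.814 | 0.769 | 4.5 |
| 1.06 | 1.5 | 0.977 | 0.811 | 0.808 | 0.3 |
| 1.786 | 0 | 0.999 | 0.997 | 0.997 | <0.1 |
| 1.786 | 0.5 | 0.994 | 0.998 | 0.994 | 0.4 |
| 1.786 | 1.0 | 0.999 | 0.998 | 0.998 | <0.1 |

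Correlation 0.7, with d still in units of the SD of change, gives nearly the same losses (10.4 points at ratio 0.5 for d = 1.06; 0.5 point for d = 1.786). So does 20 per arm. A separate run scaled to exactly 80% direct power gives 71–72% gated power at ratio 0.75. At ratio 1.25, where week 12 keeps 1/1.25 = 80% of the week-6 effect, the loss is about 1 point.

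**Step 3: 9.4.2 read literally.** With no arm term and a within-subject contrast of week 12 against baseline in 30 patients, direct power is 0.81. Gated power is 0.77, 0.70, 0.77 and 0.81 at ratios 0, 0.5, 1 and 1.5. The pattern is the same.

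**Step 4: is an effect near 80% power relevant here?** Two rows of Table 4 compare control with intervention. Knee flexion angle: d = 20.3/√((20.5² + 16.3²)/2) = 20.3/18.52 = 1.10. Vertical ground reaction force: d = 0.4/√((0.4² + 0.3²)/2) = 0.4/0.354 = 1.13. At correlation 0.5 and ratios from 0 to 1, direct power is 0.84–0.86 and the loss is 3 to 10 points. If these d values are taken in units of the SD at a single visit, correlation 0.7 reduces the loss to 0.5 to 4 points.

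**The case against.** The strongest reply is that the plan already contains a direct test. Section 9.1 permits an ungated two-sample t-test or Wilcoxon, promises standardized differences without condition, and 9.4.1 asks for p-values and confidence intervals with inferential tests. A reader might infer from 9.4.2 that the hypothesis is tested only post hoc, or that it goes untested and its estimate unreported when the overall test misses. The documents as a whole do not support that. What remains is narrower. The 9.1 sentence is permissive, leaves change versus completion value open, names no visit, and is not carried into the section headed as the primary analysis.

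A second reply is that the loss is small on the plan's own numbers. At the extension-moment proxy this is correct. That row, however, is a pre/post difference in the raw moment rather than a between-arm difference in LSI, so it does not settle the size of the effect on the endpoint.

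A third reply is that week 12 is labelled durability and training ends at week 6, so a fading effect is plausible and the gate would then cost little. That stands too.

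Finally, this is a pilot: 9.2 says significance is not its main purpose, 9.4.9 treats significant effects as exploratory, and 2.2 sets goals at both post-intervention visits, so an overall test followed by visit comparisons is a conventional choice. This lowers the weight of the power argument. It does not weaken the case for guaranteeing one defined estimate with its interval.

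**Conclusion.** The point holds in a limited form. Sections 9.1 and 9.4.2 offer two routes for the primary endpoint and neither is named as primary. Under the 9.4.2 route the hypothesised contrast passes a gate that it does not need.

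With 15 per arm and assumed compound symmetry, the cost is:
- about 4 to 11 points at an effect with about 80% direct power, if the week-6 effect is no larger than the week-12 effect;
- about 1 point if week 6 is 1.25 times week 12, and about 0.3 point at 1.5 times (a milder fade lies between 1 and 4);
- at most about 0.5 point at d = 1.79.

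A reader might take the first range as the general cost. It is not, because it depends on the pattern over visits and on an effect size that the documents do not give for the LSI. The missing arm term in 9.4.2 is a related and more serious gap. Adding the term alone would leave the conditional sentence in place, so both should be corrected together.

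**What to change.** For the primary endpoint, replace the post-hoc sentence in 9.4.2 with:

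> The between-arm difference in change from baseline to week 12 (6 weeks post intervention) in knee extension moment LSI is estimated from the mixed model with an arm-by-visit term and tested directly at two-sided 0.05, and reported with its 95% CI, whatever the overall test shows; the week-6 contrast and other visit comparisons are supportive.

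Then align the t-test sentence in 9.1, so that it refers to this contrast for the primary endpoint or is limited to other outcomes. Pointing back to the contrast in 9.1 would not be enough, because 9.1 does not choose between change and completion value.

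The cost is two wording changes made before analysis, with no new data, visits or participants. With a single pre-specified contrast, dropping the gate does not raise the error rate of that test above 0.05.
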